- 6.3.1 For induction: patients will receive sorafenib and mitoxantrone at 1 of 6 total dose levels as allocated (see section Dose Escalation Scheme page 2 or 15.1.2). Mitoxantrone will be given IV daily over 60 minutes Days 1-3 and sorafenib orally Days 10-19 for all levels. Allowances of +/- 2 days for this window will be allowed for logistical purposes. Levels are as follows: Level 1, mitoxantrone 10 mg/m² with sorafenib 200 mg PO twice daily; Level 2, mitoxantrone 12 mg/m² with sorafenib 200 mg PO twice daily; Level 3, mitoxantrone 15 mg/m² with

sorafenib 200 mg PO twice daily; Level 4, mitoxantrone 18 mg/m² with sorafenib 200 mg PO twice daily; Level 5, mitoxantrone 18 mg/m² with sorafenib 400 mg PO in the morning and 200 mg in the evening; Level 6, mitoxantrone 18 mg/m² with sorafenib 400 mg PO twice daily. Level -1, dosed at mitoxantrone 10 mg/m² and sorafenib 200 mg PO once daily will also be available for dose de-escalation due to toxicities, as described in Section 6.8. For baseline organ dysfunction within the allowable limits of the eligibility criteria, dose reduction of individual medications specific to the organ impairment (e.g. liver, kidney) are allowed but not required, as described in section 6.10, and should be done in conjunction with the Oncology Pharmacist and PI.

- 6.3.2 The dose of mitoxantrone is calculated using the patient's actual weight.
- 6.3.3 For post-remission therapy: sorafenib will be given per dose level as above, starting on day 8 until day 27 or 3 days prior to next cycle of treatment, whichever occurs first. Allowances of +/- 3 days for this window will be allowed for logistical purposes (i.e. timing of clinic visit for count evaluation).
- 6.3.4 For maintenance: sorafenib will be given daily for up to 12 months following post-remission at the final dose the patient received during induction, with subsequent dose adjustment based on blood counts and extra-medullary toxicities.
- 6.3.5 All treatment is given as intent-to-treat; missed doses will not be made up.

6.4 **Administration of G-CSF, Cladribine, and Cytarabine**

- 6.4.1 The doses of the elements of G-CLAM chemotherapy will be as follows: G-CSF 5 µcg/kg rounded to 300 or 480 µcg daily subcutaneously daily on Days 0-5, Cladribine 5 mg/m² IV daily over 2 hours on Days 1-5, and Cytarabine 2 g/m² IV daily over 2 hours on Days 1-5.
- 6.4.2 The doses of G-CSF, cladribine, and cytarabine are calculated using the patient's actual weight.

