- 6.4.3 Days 0 and 1 G-CSF may be omitted at physician discretion for WBC >20,000/µL or signs/symptoms of leukostasis.
- 6.4.4 Administration in the outpatient clinic can be considered but should be discussed with the study investigators.
- 6.4.5 All treatment is given as intent-to-treat; missed doses will not be made up.
- 6.4.6 No investigational or commercial agents or therapies other than those described herein may be administered with the intent to treat the patient's malignancy.

6.5 **Monitoring during/after Induction and Post-Remission Therapy**

For patient monitoring, the following studies and study intervals are suggested:

- 6.5.1 Complete blood counts with differential blood count, including immature cells/blast, and platelet count at least 2 times weekly until ANC >1,000/µL and then at least weekly until platelet count >100,000/µL.
- 6.5.2 Metabolic panel, including bilirubin, ALT/AST, and creatinine at least weekly until ANC >1,000/µL and platelet count >100,000/µL.

- 6.5.3** Blood pressure monitoring on a weekly basis through the first 6 weeks of therapy is recommended. Thereafter, it is recommended that blood pressure should be monitored monthly as long as the patient remains on sorafenib.
- 6.5.4** If patients develop signs or symptoms suggestive of cardiac dysfunction, LVEF should be assessed using the same method to evaluate baseline LVEF status (MUGA scan or echocardiography, or other appropriate diagnostic modality).

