6.9 Maintenance Therapy

- 6.9.1** Patients in MRDneg CR at the end of post-remission therapy with G-CLA+sorafenib can continue to receive sorafenib for up to 12 months, as long as it is tolerated and as long as an MRDneg CR is maintained. Sorafenib will be given daily at the assigned dose level, unless dose reductions are needed for toxicity, in which case that dose would be continued. The MRDneg CR state should be confirmed every 3 months with bone marrow evaluations.

6.10 Dose Modifications of Chemotherapeutic Drugs for Baseline Organ Dysfunction or Subsequent Treatment Cycles

For patients with baseline organ dysfunction within the allowed limits of the eligibility criteria, or for those who experienced \geq Grade 3 non-hematologic toxicities excluding neutropenic fever and infections during the first induction, a dose reduction is

recommended. The following dose modifications are suggested for all subsequent treatment cycles:

6.10.1 If a patient develops Grade ≥ 3 non-hematologic toxicity other than Grade 3 infections within 28 days from the last dose of G-CLAM, the next course of G-CLAM will be given once toxicity is $<$ grade 2. The following dose reductions can be considered: cladribine 4 mg/m² days 1-5, cytarabine 1.5 g/m² days 1-4, mitoxantrone at one dose level below initial regimen days 1-3, G-CSF dose unchanged, and sorafenib at one dose level below their initial regimen. Additionally, the mitoxantrone may be omitted entirely if a 2nd induction course is indicated (any response less than CR without MRD) per treating physician discretion in discussion with the PI. Assuming these doses are well-tolerated the first course of G-CLA will be administered at these doses, omitting mitoxantrone. If Grade ≥ 3 non-hematologic toxicity occurs again, there will be a further reduction in doses of cladribine to 3 mg/m² daily days 1-5 and cytarabine to 1 g/m² daily days 1-5 for the first cycle of G-CLA. Doses for subsequent courses of G-CLA will be discussed with the Principal Investigator. Patients who were receiving dose level -1 sorafenib or mitoxantrone when grade ≥ 3 toxicity occurred will be taken off study.

6.10.2 Mitoxantrone: Reduce mitoxantrone dose by 50% if the bilirubin concentration is 1.5-4.5 x IULN and to 25% if the bilirubin concentration is > 4.5 x IULN. As per 6.10.1 can omit mitoxantrone entirely if clinically indicated.

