8.4 Monitoring of Exploratory Endpoints

We will plan to assess QOL and healthcare resource utilization. Cost data will be obtained at the conclusion of study therapy

8.4.1 QOL: QOL will be assessed after each cycle of remission induction and post-remission therapy, then every 3 months if they remain on maintenance Sorafenib for up to 12 months, and at the conclusion of study treatment by the European Organization for Research and Treatment of Cancer QLQ-C30 questionnaire, a validated QOL measurement for oncology patients (Appendix C) [34]. These questionnaires will be distributed at clinic visits, which will be occurring at least monthly.

8.4.2 Cost: Cost records will be obtained at the conclusion of study treatment from the Financial Services Department.

8.4.3 Healthcare resource utilization: This will be a composite measure. These variables will be recorded (at the end of the study due to time constraints of the data coordinator) to capture the period from the start of treatment to first response assessment (e.g. remission induction). The following variables will be collected: total number of hospital admissions and duration of stays, days in the intensive care unit, number of blood product transfusions received, episodes of febrile neutropenia and days requiring antibiotic use, number of visits to the emergency department, and number of physician or advanced practice provider clinic visits.

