11.2 Definitions

11.2.1 Adverse Event (AE): Any harm or untoward medical occurrence in a research participant administered a medical product, medical treatment or procedure even if it does not necessarily have a causal relationship with the product, treatment, or procedure. An adverse event can be any unfavorable and unintended sign (including an abnormal laboratory finding, for example), symptom, or disease temporally associated with the use of a medical product, medical treatment, or procedure whether or not considered to be related. Mechanisms of obtaining information on AE include monthly transcripts, assessment forms obtained after each clinic visit, and hospital progress and discharge notes.

11.2.2 Related or Possibly Related AE: An AE is “related or possibly related to the research procedures” if in the opinion of the principal investigator, it was more likely than not caused by the research procedures. AEs that are solely caused by an underlying disease, disorder or condition of the subject or by other circumstances unrelated to either the research or any underlying disease, disorder or condition of the subject are not “related or possibly related”. If there is any question whether or not an AE is related or possibly related, the AE should be reported.

11.2.3 Serious AE (SAE): An adverse event that results in any of the following outcomes:

- Death
- Life-threatening adverse event (real risk of dying)
- Prolongation of hospitalization*
- Persistent or significant disability/incapacity/or change in psychosocial status
- Congenital anomaly
- Requirement of intervention to prevent permanent impairment of damage

*Hospitalization itself will not be considered a serious adverse event if required for complications of AML or comorbid conditions. Hospitalization will be considered a SAE if it fulfills the criteria for a serious and unexpected adverse event as otherwise described.

11.2.4 Unexpected AE: An AE is “unexpected” when its nature (specificity), severity, or frequency are not consistent with (a) the known or foreseeable risk of adverse events associated with the research procedures described in the protocol-related documents, such as the IRB-approved research protocol, informed consent document, and other relevant sources of information such as product labeling and package inserts.

11.2.5 Management of Adverse Events. Please see Appendix D for prevention/management strategies for adverse events common with sorafenib.

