Grade ≥ 3 adverse events other than hematologic toxicities will be recorded, graded, and reported as appropriate. AEs will be collected from the time of consent until 60 days after day 1 of each cycle or until the patient receives an alternative anti-cancer therapy, whichever date comes first. AEs that do not meet the requirement for expedited reporting will be reported to the IRB as part of the annual renewal of the protocol.

Myelosuppression and associated complications are expected events during leukemia therapy; therefore, myelosuppression and associated simple complications such as fever,

infections, bleeding, and related hospitalizations will not be reported as individual AE but will be summarized in the annual report to the IRB.

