Grade 1 Any occurrence	
 • Continue preventive strategies and in addition: 
 ◦ Soak hands in cool water. ◦ Apply petroleum jelly to moist skin. • In the case of hyperkeratotic lesions, exfoliate the hands or feet and apply moisturizing cream immediately afterwards.
Grade 2 Any occurrence or Grade 3 Any occurrence	
 • Continue supportive/management measures and add analgesic(s) for pain.
a: Pedicure should be done by a podiatrist.	

III. Treatment-emergent hypertension

Hypertension is a known and potentially serious AE associated with sorafenib treatment. Subjects will undergo brief physical examinations, including blood pressure monitoring, on a weekly basis through the first 6 weeks of therapy. Thereafter, blood pressure will be monitored on Day 1 of each cycle.

Blood pressure measurements considered out of the normal range are diastolic pressure > 90 mm Hg and/or systolic pressure > 140 mm Hg, or a 20 mm Hg increase in diastolic pressure if the previous measurement was within normal limits.

The dose-modification schedule to be followed in the event of treatment-emergent hypertension is outlined below. The choice of anti-hypertensive medication to be used in cases of treatment-emergent hypertension will be at the investigator's discretion and based on site-specific treatment guidelines as applicable. All anti-hypertensive medications used for the management of treatment-emergent hypertension should be recorded in the subject's records.

Once a dose-reduction modification has been made for treatment-emergent hypertension, NO dose re-escalation will be allowed.

Management of Treatment-Emergent Hypertension	
Grade of Event (NCI-CTCAE v4.0)	Management/ Next Dose
Grade 1	Consider increasing blood pressure monitoring. Continue sorafenib dosing as scheduled.
Grade 2 asymptomatic and diastolic pressure 90-99 mm Hg	Begin anti-hypertensive therapy. Continue sorafenib dosing as scheduled.
Grade 2 (symptomatic/persistent) OR Grade 2 symptomatic increase by > 20 mm Hg (diastolic) or to > 140/90 mm Hg if previously within normal limits OR Grade 3	Sorafenib should be held ^a until symptoms resolve and diastolic blood pressure < 90 mm Hg; also treat subject with anti-hypertensives and when sorafenib is restarted, reduce by 1 dose level. ^b If diastolic blood pressure is not controlled (< 90 mm Hg) on anti-hypertensive therapy, reduce another dose level. ^b

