Grade 4	Discontinue sorafenib

a: Subjects requiring a delay of > 30 days (modify according to study specific cycle length) should discontinue sorafenib unless, in the opinion of the treating physician, the subject may benefit from continued treatment.

b: Subjects requiring dose reductions beyond 200 mg (1 placebo tablet) twice daily, every other day, should discontinue sorafenib.

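### The adverse event collection window ends 60 days after day 1 of each cycle, but no cycle is defined for up to 12 months of sorafenib maintenance, so routine Grade 3 or higher recording there is ambiguous and may stop early

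*Combined protocol and SAP*

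**What the plan says.** Section 11.2.5 states that "AEs will be collected from the time of consent until 60 days after day 1 of each cycle". Other anti-cancer therapy ends collection if it comes first. The same paragraph limits routine recording to Grade 3 or higher events other than hematologic toxicity. No other section sets a collection period.

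Maintenance is described twice. Section 6.3.4: "sorafenib will be given daily for up to 12 months following post-remission". Section 6.9.1: patients in MRD-negative CR "can continue to receive sorafenib for up to 12 months, as long as it is tolerated". Neither gives a cycle length, a day 1, or a start day relative to the last G-CLA course.

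Other sections use the word cycle in different ways:

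- Section 8.4.1 ties it to chemotherapy and puts maintenance on the calendar: "QOL will be assessed after each cycle of remission induction and post-remission therapy, then every 3 months if they remain on maintenance Sorafenib".
- Section 6.5.3, on blood pressure after the first 6 weeks: "it is recommended that blood pressure should be monitored monthly as long as the patient remains on sorafenib". Section 6.13 also schedules maintenance laboratory tests and blood pressure by calendar month.
- Appendix D, part III, on the same checks: "Thereafter, blood pressure will be monitored on Day 1 of each cycle". Footnote a to its table still carries a template instruction: "modify according to study specific cycle length".

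Section 11.2.1 names the sources of adverse event information: "Mechanisms of obtaining information on AE include monthly transcripts, assessment forms obtained after each clinic visit". It does not say for how long they are to be used.

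**The concern.** A collection window tied to a cycle works only while there are cycles. During maintenance the patient takes study drug every day for up to a year, but the event that sets the window has no defined counterpart. Staff could close collection soon after the last G-CLA course, 60 days into maintenance, or not until maintenance ends, and could do so differently for different patients.

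What is at stake is the record of expected Grade 3 or higher non-hematologic toxicity on maintenance. Hypertension, hand-foot reaction and liver toxicity, for example, are listed sorafenib effects. Such an event could appear in the clinic notes without entering the adverse event dataset. Two uses of that dataset are exposed. One is secondary objective 2.2.2, the toxicity profile and adverse event rate. The other is the review in section 14.1.1, which looks across all phase 1 patients for late and cumulative toxicity before phase 2 opens and may lead to lower doses. That review is affected only for phase 1 patients who have reached maintenance by then.

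**Working it through.** The plan states no derived figure here, so there is none to reproduce. The check is a day count.

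**Inputs.** The window is day 1 plus 60 days, so its last day is day 61 of the governing cycle (section 11.2.5). Maintenance length L is up to 12 months, taken as 365 days (sections 6.3.4, 6.9.1). The maintenance start, day s of the last G-CLA course, is not in the documents and is varied as an assumption.

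**Reading 1: the last G-CLA course governs.** Covered days = 62 − s for s up to 61, otherwise 0. Share outside = (L − covered) / L.

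| Start day s | Covered days | Share of 365 days outside |
|---|---|---|
| 28 | 34 | 331/365 = 90.7% |
| 42 | 20 | 345/365 = 94.5% |
| 49 | 13 | 352/365 = 96.4% |
| 62 or later | 0 | 365/365 = 100% |

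Shorter maintenance lowers the share. For L = 90 it is 56/90 = 62.2% with s = 28, 70/90 = 77.8% with s = 42, and 100% with s = 62 or later.

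**Reading 2: maintenance is one cycle with its own day 1.** Covered days = 61. Share outside = 304/365 = 83.3%, or 29/90 = 32.2% for a 90-day maintenance.

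**Reading 3: maintenance runs in repeated cycles.** With cycles of 60 days or less, each window reaches into the next cycle and 0% is outside. The result depends on the assumed length. With 91-day cycles, four full cycles lose 91 − 61 = 30 days each, so 120/365 = 32.9% is outside.

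**Which reading the text favors.** Section 8.4.1 separates cycles from maintenance, and section 6.13 schedules maintenance by calendar; both point to reading 1. Reading 2 has no direct support. Monthly cycles can be inferred only by setting section 6.5.3 (monthly checks) beside Appendix D (checks on day 1 of each cycle). Appendix D defines no cycle and contains an unfilled template note, so it is weak support.

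**Check of the proposed 30-day tail.** Last scheduled induction dose: day 19, or day 21 with the allowed 2-day shift; adding 30 gives day 49 or 51. Last scheduled post-remission dose: day 27, or day 30 with the allowed 3-day shift; adding 30 gives day 57 or 60. All fall before day 61. A later-of rule with a 30-day tail therefore leaves the window unchanged for patients who never start maintenance and take sorafenib within the scheduled windows. A tail above 31 days would not: 30 + 32 = day 62.

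**The case against.** The strongest reply is that the 60-day limit may be deliberate. Objective 2.2.2 concerns sorafenib in combination with G-CLAM, and maintenance is sorafenib without concurrent chemotherapy. This partly stands: the objective does not settle whether maintenance belongs to it. But the protocol nowhere says that maintenance is left out of adverse event recording, and section 14.1.1 asks for late and cumulative toxicity without a time limit.

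The second reply is that safety on maintenance is watched in other ways. This is true, and a reader should not infer that such toxicity goes unmonitored or unreported:

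- Section 6.13 recommends blood tests and blood pressure at least monthly.
- Expedited reporting (section 11.1) has no end date.
- Section 12.0 provides study-team review of adverse events and at least annual committee review.
- Section 6.14 requires reasons for stopping treatment to be documented.
- Appendix D requires antihypertensive drugs given for treatment-emergent hypertension to be recorded.
- Section 8.5 follows survival.

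None of these sets a collection period for expected Grade 3 or higher events. Expedited reporting needs an event that is unexpected, related or possibly related, and serious or indicative of greater risk. An ordinary Grade 3 case of a listed effect would not usually qualify.

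A reader might also take a single figure, such as 95% of the year, as what the protocol loses. The documents do not support this. That figure needs both reading 1 and a start near day 42, and no section gives a start day.

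**Conclusion.** The concern holds as an ambiguity with a likely gap. The only rule for routine Grade 3 or higher non-hematologic recording depends on a cycle that maintenance does not have. On the best-supported reading, and assuming a start between day 28 and day 62 or later, about 91% to 100% of a full maintenance year is outside the window. The other readings give about 83% (one cycle) and 0% (cycles of 60 days or less).

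These are shares of maintenance time for one patient, not shares of events lost. The documents do not say how many patients will start maintenance, and transplantation or recurrence of MRD ends treatment, so the effect on trial-level adverse event rates cannot be sized. Hematologic toxicity is outside this recording in any case. The primary endpoint, MRD-negative CR after up to 2 induction courses, and the Cycle 1 dose-limiting toxicities are not affected. The change is worth making because it is cheap, not because the main results depend on it.

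**What to change.** Amend section 11.2.5 so that Grade 3 or higher non-hematologic events are collected until the later of (a) 60 days after day 1 of the last chemotherapy cycle and (b) 30 days after the last sorafenib dose, including maintenance. Other anti-cancer therapy should still end collection if it comes first. The 30 days is a choice, close to the 61 − 27 = 34 days that the present rule leaves after the last scheduled post-remission dose.

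Define cycle once, and reconcile sections 6.5.3, 8.4.1 and 11.2.5 with Appendix D, part III, and its footnote a. State whether objective 2.2.2 covers maintenance. If it does, it would help to report maintenance events separately, with the number of patients who started maintenance.

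The cost is modest extra data entry, only for patients on maintenance, from visits and information sources already planned (sections 6.13, 8.4.1, 11.2.1). Section 8.4.3 notes limits on data coordinator time, which is a reason to keep the extension to Grade 3 or higher non-hematologic events.

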2.2 Secondary Objectives

- 2.2.1 To estimate rates of CR, ORR, OS, EFS, and relapse-free survival (RFS) after the addition of sorafenib to G-CLAM in patients with newly-diagnosed AML/high-risk MDS.
- 2.2.2 To describe the toxicity profile and safety (rate of adverse events) of sorafenib in combination with G-CLAM.

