6.13 Recommended Follow-up Care

6.13.1 For patients who continue to receive sorafenib for up to 12 months after the completion of G-CLA+sorafenib, they should have complete blood counts and a metabolic panel (to include kidney and liver function) done at least monthly and a bone marrow exam every 3 months, including after the completion of sorafenib.

6.13.2 While still on sorafenib, blood pressure should be monitored at least monthly.

6.13.3 After completion of protocol treatment, patients should be evaluated by treating physicians according to institutional and/or national guidelines or the discretion of the attending physician. These evaluations may include peripheral blood studies and/or bone marrow examinations, as clinically indicated.

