7.4.3 Adverse Effects: The most common adverse reactions (> 20%) for sorafenib are diarrhea, fatigue, infection, alopecia, hand-foot skin reaction, rash, weight loss, decreased appetite, nausea, gastrointestinal and abdominal pains, hypertension, and hemorrhage. When used in combination with chemotherapy for treatment of AML, the most common adverse reactions thought to be related to the addition of sorafenib include hyperbilirubinemia/transaminitis, nausea/vomiting, diarrhea, rash, hand-foot syndrome, pancreatitis/colitis, and cardiac/hypertension. Please see Appendix F for management of adverse events specific to sorafenib.

7.4.4 Administration: Subjects will be instructed on the proper administration of sorafenib. Sorafenib tablets should be taken 12 hours apart, at approximately the same time each morning and evening. Sorafenib tablets should be taken without food, at least 1 hour before or at least 2 hours after a meal, and with up to 240 mL (approximately 1 cup or 8 oz.) of water. Consumption of grapefruit and grapefruit juice should be avoided while receiving study drug. If a dose of sorafenib is missed, the next dose should be taken at the regularly scheduled time.

7.4.5 Drug-Drug Interactions: Strong CYP3A4 inducers (such as carbamazepine, dexamethasone, phenobarbital, phenytoin, rifampin, rifabutin, St. John's wort) can decrease systemic exposure to sorafenib, and concomitant use of these medications should be avoided whenever possible. Concomitant use of strong CYP3A4 inhibitors (such as azithromycin, ketoconazole, ritonavir) may be allowed, but patients should be closely monitored for signs/symptoms of toxicity from increased exposure to sorafenib.

Interactions with strong CYP3A4 inhibitors has not been well studied, although ketoconazole administered at 400 mg once daily for 7 days did not alter the mean AUC of a single oral dose of sorafenib 50 mg in healthy volunteers.

7.4.6 Storage and Stability: Sorafenib tablets do not need to be protected from light. They are sufficiently stable with regard to light, oxidation, thermal stress, and hydrolytic degradation. The formulation is presented as an immediate release (IR) dosage form, i.e., the active ingredient is completely dissolved under in vitro test conditions within a short period of time.

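### The adverse-event collection window is tied to cycles, but maintenance sorafenib is not defined as cycles, so up to 12 months of study drug may fall outside routine AE collection

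*Combined protocol and SAP*

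**What the plan says.** Section 11.2.5 limits routine recording to grade 3 or higher events other than hematologic toxicities and sets the period: "AEs will be collected from the time of consent until 60 days after day 1 of each cycle". Collection closes sooner if the patient moves to a different treatment for the leukemia.

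Maintenance is part of the treatment plan. Section 6.3.4 states: "For maintenance: sorafenib will be given daily for up to 12 months following post-remission". Section 6.9.1 adds that patients in MRD-negative CR after post-remission therapy "can continue to receive sorafenib for up to 12 months, as long as it is tolerated". Neither section divides this year into cycles. Section 8.4.1 keeps the two ideas apart: "QOL will be assessed after each cycle of remission induction and post-remission therapy, then every 3 months if they remain on maintenance Sorafenib".

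The safety objective, 2.2.2, is "To describe the toxicity profile and safety (rate of adverse events) of sorafenib in combination with G-CLAM". The sorafenib part of section 7 lists, among the commonest reactions attributed to adding the drug to AML chemotherapy, "hand-foot syndrome, pancreatitis/colitis, and cardiac/hypertension".

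During maintenance, 6.13.1 recommends that "they should have complete blood counts and a metabolic panel (to include kidney and liver function) done at least monthly", and 6.13.2 asks for blood pressure at least monthly while sorafenib continues. After treatment, 8.5 follows patients for up to 5 years but names only EFS, RFS and OS.

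**The concern.** The window moves forward each time a cycle starts. That works for induction and post-remission therapy, where each course has a day 1. It does not plainly work for maintenance, which is continuous dosing with no stated day 1. Taken literally, the last window opens with the last post-remission cycle and closes 60 days later, while the patient may go on taking sorafenib for most of a year.

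Sorafenib is the drug under test, and the protocol expects hypertension, cardiac effects and hand-foot reaction from it. If maintenance events are not routinely recorded, the reported adverse-event rate would describe the chemotherapy phase well and the long sorafenib phase poorly. A reader of the final report could not tell. Two staff members could also apply the same sentence differently, one counting maintenance months as cycles and the other not.

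**Working it through.** The plan gives no figure for AE coverage of maintenance, so there is none to reproduce. The check is a count of days.

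**Inputs**
- Window: 60 days after day 1 of a cycle (11.2.5).
- Maintenance: daily, up to 12 months, taken as 365 days (6.3.4, 6.9.1).
- Sorafenib days: 10 per induction course (days 10-19) and up to 20 per post-remission course (days 8-27), with up to 4 post-remission courses (dose tables, 6.3).
- Assumption: maintenance starts 28 to 49 days after day 1 of the last post-remission cycle. The plan gives no interval. The lower end is about when that cycle's sorafenib stops (day 27). The upper end matches the day-49 limit for persistent aplasia in 6.14.5.

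**Reading A: maintenance is not a cycle**
- Days covered = 60 - start: 60 - 28 = 32, or 60 - 49 = 11.
- Days not covered = 365 - covered: 365 - 32 = 333 (333/365 = 91%), or 365 - 11 = 354 (354/365 = 97%).
- A start 60 or more days after day 1 would leave nothing covered.

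**Reading B: maintenance is one cycle**
- Covered: 60/365 = 16%.

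**Reading C: each maintenance month is a cycle**
- Each 60-day window overlaps the next, so coverage is complete.

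**Share of all sorafenib days under reading A**, for a patient who completes four full post-remission courses and the full year:
- Before maintenance: 10 + 4 × 20 = 90 days with one induction; 20 + 4 × 20 = 100 days with two.
- Not covered: 333/(365 + 100) = 72%, up to 354/(365 + 90) = 78%.

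**Which reading does the text favor?** Section 8.4.1 uses cycle for induction and post-remission therapy and then turns to maintenance in calendar months, which supports A. Section III of Appendix D schedules blood pressure weekly for 6 weeks and then on the first day of every cycle. Section 6.5.3 gives the same weekly start followed by monthly checks for as long as sorafenib continues. Put together, these allow C. However, Appendix D carries unadapted template text. One footnote tells the user to adjust a limit to the study's cycle length, and another mentions a placebo tablet, although this study is open-label with no placebo arm. It makes the wording ambiguous without settling it.

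**The case against.** The strongest reply is that this is an ambiguity, not a proven omission, and that maintenance events would surface anyway. Section 11.2.1 draws AE information from monthly transcripts, post-visit assessment forms and hospital notes. Section 8.4.1 expects clinic visits at least monthly. Appendix D wants antihypertensive use recorded. Section 6.14.7 documents toxicity that ends treatment. Expedited reporting (11.1) has no end date, and 11.2.2 says to report when relatedness is in doubt.

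Much of this stands: events would probably be seen. But none of these provisions extends the collection period in 11.2.5. Expedited reporting requires the event to be unexpected, and hypertension and cardiac effects are listed risks, so ordinary cases would usually not qualify, although excess severity or frequency could (11.2.4). Section 6.14.7 does not reach a grade 3 event managed by a hold or dose reduction. The pre-phase 2 review in 14.1.1 covers phase 1 patients only and adds no collection time.

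It can also be said that 2.2.2 concerns sorafenib combined with G-CLAM, whereas maintenance is sorafenib alone. That is a fair literal reading. Maintenance is nonetheless protocol treatment with the study drug, and reporting it separately answers the point.

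A reader might go further and infer that late cardiac toxicity from mitoxantrone is missed, since two full inductions give 3 × 15 × 2 = 90 mg/m² at level 3 and 3 × 18 × 2 = 108 mg/m² at levels 4-6, against the 80-100 mg/m² mentioned in the mitoxantrone drug information. The documents do not support this as a stated defect. The window restarts with each later cycle. Many patients leaving after failed induction would presumably move to other anti-cancer therapy, where stopping collection is sensible for attribution. A total of 90 mg/m² lies within the band and only 108 is above it. The number of patients with two full inductions, no later cycle and no other therapy cannot be sized.

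**Conclusion.** The point holds for maintenance. Followed as written, with cycle meaning what it means in 8.4.1, the AE window leaves 333 to 354 of 365 maintenance days (91-97%) outside routine collection for a patient who completes 12 months, given the assumed start at 28 to 49 days. Counting maintenance in monthly cycles removes the gap, so coverage runs from about 3% to 100% depending on a word that the plan does not define.

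A reader might take 91-97% as a share of patients or events. It is a share of days for someone who completes the maximum duration. The number entering maintenance is unknown, transplant takes patients off treatment before then (6.14.2), and the documents give no rate from which missed events could be computed. Nor do they show that staff have stopped recording maintenance events; they show only that the text does not require it.

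The consequence is confined to the completeness of the toxicity profile in 2.2.2. The MTD, DLT rules, Simon boundaries, primary endpoint and sample size do not change. The sponsor should still correct it, because it concerns safety data on the drug under test and the remedy is small.

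**What to change.** Amend 11.2.5 so that grade 3 or higher non-hematologic events are collected from consent until the later of two dates: 60 days after day 1 of the last chemotherapy cycle, or the end of maintenance sorafenib plus a short set period (for example 30 days). Keep the existing stop at alternative anti-cancer therapy. Report maintenance-phase events separately from those during G-CLAM and G-CLA cycles, and state the collection window in the safety report. For patients already past the current window, recover events retrospectively from records and say so.

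The cost is an IRB-reviewed wording change and a little more AE recording. Visits already occur at least monthly, with blood tests and blood pressure checks, so no new visit or test is needed. Retrospective recovery will be less complete than prospective recording.

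Optionally, the record review contemplated in 8.5 could also abstract heart failure and any LVEF results obtained in routine care. This is not needed to resolve the point.
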